14. ETHICAL AND REGULATORY CONSIDERATIONS

14.1. MAINTAINING RECORDS (21 CFR 812.140 (B))
14.2. INSTITUTIONAL REVIEW BOARD (IRB) / ETHICS COMMITTEE (EC) INFORMATION

15. CLINICAL CENTERS

16. DATA HANDLING

17. DATA ANALYSIS

REFERENCES

PROTOCOL SUMMARY

Title: **Intramural Needle Ablation for the Treatment of Refractory Ventricular Arrhythmias**

Objective: This study will examine the safety and efficacy of intramural needle ablation (INA) in the treatment of intramural ventricular arrhythmias in patients for whom standard RF ablation has been unsuccessful. We hypothesize that the increased current density and improved rates of transmural lesion creation seen with intramural needle ablation will lead to successful arrhythmia termination with minimal or no increased risk of complication.

Design: This is a prospective, single-center, non-randomized, un-blinded, observational trial.

Enrollment: Eligible subjects will be consented for participation in the trial prior to undergoing ablation. Patients are considered eligible to undergo intramural needle ablation if they meet the following criteria 1) a) monomorphic ventricular tachycardia (VT); b) frequent ventricular arrhythmia (including unifocal PVCs, couplets, or nonsustained VT) with a PVC burden $\geq 13\%$, or is causing a decline in left ventricular (LV) ejection fraction to $\leq 40\%$; or c) previous failed ablation for one or more of the criteria above, 2) Age 16 or older; 3) Left ventricular (LV) ejection fraction $> 10\%$ as estimated by echocardiography, contrast ventriculography or radionuclide imaging within the past 90 days; 4) Clinical indication for catheter ablation of VT; 5) Ventricular arrhythmias not terminable with standard ablation once enrolled in the Intramural Needle Ablation study or previous failed ablation within 6 months prior to enrollment; 6) Able and willing to comply with all pre-, post-, and follow-up testing and requirements; 7) Signed informed consent (for patients < 18 years old, parental consent will be obtained with patient assent); 8) Projected lifespan greater than 1 year.

Patients will be excluded from the trial if: 1) history of MI or CABG within 6 weeks; 2) Class IV HF; 3) Idiopathic ventricular arrhythmias defined as VT or PVCs that occur without evidence of structural heart disease and that are not causing significant depression of LV function; 4) pregnant; 5) Definite protruding left ventricular thrombus on pre-ablation echocardiography or other imaging modalities; 6) contraindication to heparin; 7) allergy to radiographic contrast dye; 8) unstable angina that is not due to frequent or incessant VT; 9) acute non-cardiovascular illness or systemic infection; 10) thrombocytopenia (platelet count $< 50,000 \text{ mm}^3$) or coagulopathy; 11) cardiogenic shock unless it is due to incessant VT; 12) unable to sign consent; 13) projected lifespan of < 1 year. Patients are considered enrolled once consented. Patients who do not undergo ablation of ventricular arrhythmias within 90 days of enrolling will be considered to be screen failures. Patients successfully terminated with standard ablation once enrolled will be followed in a registry for 6 months, (adhering to the same post-procedure schedule as the patients that underwent intramural needle ablation). Two hundred subjects are

	expected to be enrolled in the study.
Clinical Sites:	Mount Sinai Hospital, New York, NY
Time Course:	Expected duration of patient enrollment is approximately 2 years.
Subject Description:	Subjects will only be eligible for this study if they are \geq 16 years of age and have a history or suspected history of ventricular arrhythmias.
Primary Endpoints:	
 1. Freedom from recurrent ventricular arrhythmias at 6 months 2. Procedural complications (death, stroke, myocardial infarction, heart failure, conduction abnormalities, pericardial effusion requiring drainage, hematoma, pseudoaneurysm)
Secondary Endpoints:	
 1. Post-ablation inducibility 2. Time to termination 3. Total duration of intramural needle ablation 4. All-cause mortality
	(For patients who have been re-enrolled after the six-month follow-up is complete, primary and secondary endpoints will be re-assessed at six months post-second procedure.)
Primary Analytical Analysis:	N/A
Secondary Analytical Analysis:	N/A
Study Sponsor:	[name]. Icahn School of Medicine at Mount Sinai [name]

2 STUDY OBJECTIVE

This prospective, single center observational study will examine the role of intramural needle radiofrequency (RF) ablation for the treatment of intramural ventricular arrhythmias in patients who have failed standard RF ablation. We hypothesize that the increased current density and improved rates of transmural lesion creation seen with intramural needle RF ablation will lead to successful arrhythmia termination with minimal or no increased risk of complication.

3 INTRODUCTION, RATIONALE

Radiofrequency (RF) ablation is the most commonly employed method for the catheter treatment of cardiac arrhythmias. Myocardial scar serves as the most frequent substrate for the genesis of both atrial and ventricular arrhythmias. Such scar frequently contains surviving myocyte bundles interspersed with fibrotic tissue, which leads to slow conduction. Areas of denser fibrosis cause conduction block. When appropriately arranged, conduction through or around these scars leads to the creation of a “reentry” circuit through which an arrhythmia is generated and maintained.¹ Each reentry circuit contains within it an area called the isthmus, a portion of the circuit located in a position intimately related to the scar border zone. Electrical activation travels slowly through the isthmus before breaking out into normal myocardium. Ablation at the site of an isthmus will terminate a reentrant tachycardia.²

RF ablation is also commonly used for the treatment of isolated premature ventricular contractions (PVCs), couplets, and non-sustained VT that occur in patients without structural heart disease. However, when frequent, ventricular ectopy can result in left ventricular dysfunction and increased risk of congestive heart failure. PVC-induced cardiomyopathy appears to be a distinct entity from tachycardia-induced cardiomyopathy. Patients who develop cardiomyopathy have overall heart rates similar to those with PVCs who do not develop LV dysfunction.³ But higher PVC burdens clearly portend greater risk for cardiomyopathy. One study reported a 24% PVC burden to have the best combination of sensitivity and specificity in identifying patients likely to develop cardiomyopathy, though LV function improvements occur following catheter ablation with PVC burdens as low as 10%.⁴ In a four-center study, a 13% PVC burden predicted, with 100 percent sensitivity and 85 percent specificity, an absolute increase of 5% in the LV ejection fraction after catheter ablation.²¹

A variety of techniques, including electroanatomic mapping and activation, entrainment, and substrate mapping, are employed during electrophysiologic (EP) study to identify areas of myocardial scar and potential isthmus sites. Points or lines of ablation using RF energy are then created in an attempt to interrupt the reentry circuit. Similarly, activation or pace-mapping is also used to identify the site of origin of PVCs. Typically, RF energy is applied via a catheter tip electrode to the endocardial or epicardial surface of the heart and grounded via an electrode pad placed on the patient's skin. RF energy in this setting is dispersed through the entirety of the tissue between catheter tip and grounding pad. The standard 7-French, 4-mm tip catheters are highly successful at ablating circuits located within a few millimeters of the catheter tip. A focal, 1mm area of resistive heating occurs within the myocardium immediately in contact with the catheter tip; myocardial cell death occurs several millimeters more deeply through passive, conductive heating, which spreads outward from the contact point.⁵

While the standard catheter is effective at the ablation of superficial arrhythmias, it has proven more problematic when used for deep myocardial sites or for creating transmural lesions. A number of alternatives have been developed in an attempt to access these sites. 8-mm or 10-mm catheter tips are able to create larger zones of resistive heating, delivering direct RF energy to a larger area of myocardium. A larger interface between catheter tip and blood improves cooling and allows for the delivery of more power without a rise in impedance.⁶ The clinical use of these larger catheters can, however, be limited by rapid temperature rises at the catheter-tissue interface, resulting in thrombus formation, char, and "steam pop" rupture of the endocardial surface.⁷ The use of irrigated ablation catheters have improved upon the ability to deliver RF energy without a sustained rise in impedance. Both open irrigated- and closed-loop irrigated catheters circulate saline along the catheter tip-myocardial interface, allowing for continued delivery of RF current without thrombus formation at the endocardial surface. Intramyocardial temperature rises accordingly without a concomitant endocardial temperature surge, creating larger and deeper myocardial ablation zones.⁸⁻¹² Transcoronary ethanol ablation has also been employed with moderate success in patients with arrhythmias resistant to endocardial catheter ablation.¹³ This technology, however, grants only limited control over the size of the resulting infarct and is restricted by the need for perfusion of the scar zone by an accessible coronary artery.

Nevertheless, there remain occasions in which an arrhythmia cannot be eliminated by standard ablation techniques. This is seen most frequently due to deep intramural ventricular tachycardia, sometimes encountered following myocardial infarction. Both standard and alternative ablation strategies are frequently either unavailable or inadequate for termination of these arrhythmias.

Initial experience with an electrically active needle electrode have demonstrated that radiofrequency ablative energy can effectively create lesions of homogeneous necrosis.¹⁴ Needle electrodes have been used experimentally from the epicardial surface, from the endocardium *ex vivo* and *in vivo* in an internally irrigated form.¹⁵⁻¹⁸ It has been shown that the use of a narrow-gauge non-irrigated endocardial needle ablation catheter creates very narrow but deep lesions due to the small electrode size.¹⁹ Catheters featuring a retractable needle tipped electrode with intramyocardial saline infusion have also shown promise as a means of accessing deep myocardial circuits in ventricular tachycardia ablation.²⁰

The proposed study will further examine the role of INA in patients with ventricular arrhythmias resistant to standard ablation techniques.

4 DEVICES AND PROCEDURES

4.1 HARDWARE / SOFTWARE / CATHETERS

The needle-tipped ablation catheter is a deflectable catheter with a distal bipole (dome and ring electrodes) with an extendable/retractable 27-gauge nitinol needle. The needle has a central lumen through which saline can be infused. It has an embedded thermocouple and a position sensor within the tip which is compatible with an electroanatomic mapping system (Carto; Biosense Webster). The needle can be extended or retracted to adjust the depth. It can be locked in position at the desired depth. In its fully retracted position, it is entirely within the catheter tip, whereas, when fully deployed, it extends 12 mm beyond the tip. The depth of extension can be preset and the needle can be locked in position with an adjustable plunge activator. During catheter manipulation, the needle is kept retracted and irrigated with 0.9% saline (with 2 U/mL heparin) at 1 mL/min.

Recording and pacing are possible from both the external electrodes and from the needle. Bipolar recordings are generated between the needle and ring electrode (filtered 30–500 Hz), and between the needle and an inferior vena cava electrode, as well (filtered 30–500 Hz, and separately, filtered 0.5–500 Hz).

At target sites of VT circuits, the catheter tip is placed roughly perpendicular to the endocardial surface. Infusion is discontinued and the needle is extended 7 to 9 mm into the myocardium. One ml of infusate (50% NaCl solution [with 2U/mL heparin], 50% iopamidol [76%]) is injected into the myocardium, after which heparinized saline (2 U/mL, 0.9% NaCl) is infused at 1 mL/min for 60 s. Myocardial staining with contrast is confirmed with fluoroscopy to ensure intramyocardial positioning and to rule out perforation. Temperature-controlled power is delivered for 60 to 90 s with temperature limited to 60°C and power limited to <35 W.

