4.2 ABLATION PROCEDURES

Standard Ablation Technique for Ventricular Arrhythmias:

The standard ablation procedure will be performed using the Biosense-Webster Thermocool SF catheter (Diamond Bar, CA, USA). Hemodynamic support to allow for entrainment mapping may be employed with either an intra-aortic balloon pump or with a percutaneous left ventricular assist device. All mapping will be performed with a hybrid magnetic/impedance-based mapping system (Carto, Biosense Webster, Diamond Bar, CA). LV endocardial and epicardial mapping will be performed by utilizing a transseptal and subxiphoid puncture approach, respectively. Prolonged, split, or isolated late potentials will be tagged. For unipolar RF, power will be set to 30–50 W at 30-cm³ irrigation, targeting an impedance drop of >10 Ω. In the epicardium, power will be set to 15–30 W with 5-ml/min irrigation. The use of the percutaneous left ventricular assist device in patients with ventricular tachycardia (VT) allows for prolonged mapping during VT. Termination during VT will therefore be the preferred initial strategy for these patients, followed by substrate modification. The procedural end point will be non-inducibility of VT.

Intramural Needle Ablation of Ventricular Arrhythmias:

INA will be performed with Intramural Needle Ablation catheter, a retractable needle-tipped catheter (Biosense Webster, Inc., Diamond Bar, CA, USA). The catheter will be positioned at locations determined on the basis of activation or entrainment mapping. Saline solution (0.9% NaCl, 19°C) will be infused through the needle into the myocardium at 1 mL/min for 60 seconds using an automatic injector (Mark V, Medrad, Pittsburgh, PA, USA). Ablation will be initiated with RF energy (500 kHz, Stockert-70 RF Generator, Stockert GMBH, Freiburg, Germany) which will be delivered between the needle and a skin patch electrode. Power will be manually titrated between 30-50 W (limiting catheter tip temperatures to < 60°C) over 60-90 seconds for an impedance drop of up to 30-40 Ω. Ablation will be terminated or the power down-titrated if a sudden rise in temperature or a rapid fall or rise in impedance is seen.

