6 ENDPOINTS

6.1 Primary Endpoint

1. Freedom from recurrent ventricular arrhythmias at 6 months, defined as sustained ventricular tachycardia lasting longer than 30 seconds or a decrease in ventricular arrhythmias (defined as unifocal PVCs, couplets, non-sustained VT) to less than 5000 ventricular beats per 24 hours and identified due to clinical symptoms, device interrogation, or 24-hour ambulatory monitoring.
2. Procedural complications (death, stroke, myocardial infarction, heart failure, conduction abnormalities, pericardial effusion requiring drainage, hematoma, pseudoaneurysm)

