10.3 VT ABLATION PROCEDURAL DETAILS

- Patients will be brought to the electrophysiology laboratory in a fasting state.
- General anesthesia or conscious sedation will be used for sedation.
- Patients will undergo electrophysiology study and VT ablation as per standard practice.
- If a patient's arrhythmia cannot be eliminated with standard ablation or if the patient has failed ablation by standard technique, the patient will undergo INA. The INA hardware/software will be employed as described above.
- Therapeutic anticoagulation will be administered with intravenous heparin with a target ACT of 300 seconds or greater.
- Esophageal temperature monitoring is required when ablation is performed in the coronary sinus or epicardium irrespective of whether standard ablation or intramural needle ablation is performed. Ablation should be stopped when esophageal temperature is $\geq 38.5^{\circ}\text{C}$.
- Procedural endpoint will be non-inducibility of clinical VT.

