To meet the study's ethical responsibility to its subjects, an independent Data Monitoring Committee (DMC) will monitor results during the study. The committee will consist of a cardiologist who has no formal involvement or conflict of interest with the subjects, the investigators, the sponsor or the DCC. The DMC will act in a senior advisory capacity to the DCC regarding data and safety matters throughout the duration of the study. In addition, the DMC will review interim summary results of the accumulating data every 6 months or on an as needed basis depending on enrollment figures. These data include adverse events (e.g., infection, bleeding, right heart failure) and mortality. They will communicate their findings directly with the DCC. The FDA will be provided a copy of any written

communication from the DMC to the study sponsor related to safety concerns within 10 days. FDA will also be notified within 10 days if the DMC requires changes to the study protocol, procedures or informed consent document. The DMC will be provided a copy of any letter from the FDA to the study sponsor related to safety concerns, or changes to the study protocol, procedures or informed consent document. The clinical centers will have no contact with the members of DMC regarding this trial and no voting member of the committee may participate in the study as an investigator. Non-DMC members will not be allowed during DMC closed meetings.

Interim Analyses

An interim analysis will be performed after the enrollment of 20 subjects. This analysis will be presented to the DMC, who has the authority to terminate the study prematurely if an increase in adverse events is encountered. If the DMC determines the trial should be stopped early because of safety concerns, or otherwise modified, the DMC will prepare formal written recommendations to the PI to consider final action. Moreover, any pressing safety concerns that the DMC identifies will be verbally communicated to the PI as soon as possible, prior to written documentation. The trial will be terminated early if severe procedure-related adverse events occur in more than 15% of patients.

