13.3 Deviations from Protocol

The investigator will not deviate from the protocol except in medical emergencies or in unforeseen, isolated instances where minor changes are made that will not increase the patient's risk or affect the validity of the trial. In medical emergencies, prior approval for protocol deviations will not be required, but the IRB/EC must be notified within five days of the incident.

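### Sections 4.1 and 4.2 set different power limits for the same investigational needle, so an application at 35–50 W is allowed by one and barred by the other

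*Combined protocol and SAP*

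**What the plan says.** Section 4.1 describes the needle catheter and then the steps at a target site. On energy delivery it says: "Temperature-controlled power is delivered for 60 to 90 s with temperature limited to 60°C and power limited to <35 W". It gives no lower bound on power.

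Section 4.2, in the paragraph on intramural needle ablation, states that energy passes between the needle and a skin patch, and then: "Power will be manually titrated between 30-50 W (limiting catheter tip temperatures to < 60°C) over 60-90 seconds". It adds a safeguard: "Ablation will be terminated or the power down-titrated if a sudden rise in temperature or a rapid fall or rise in impedance is seen".

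Section 10.3, which sets out the procedure, refers back in one sentence: "The INA hardware/software will be employed as described above". It repeats neither power rule.

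Section 13.3 begins: "The investigator will not deviate from the protocol except in medical emergencies". It goes on to allow unforeseen, isolated minor changes that neither raise patient risk nor affect the trial's validity. It does not say which section prevails when two conflict.

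**The concern.** Power is a core setting of the treatment under test. If its upper limit is stated in two ways, an operator, a monitor and a Data Monitoring Committee member can each read the protocol correctly and disagree on whether a given application followed it. A 40 W application complies with Section 4.2 and breaches Section 4.1.

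Procedural complications are a primary endpoint in Section 6.1, and Section 11 says: "The trial will be terminated early if severe procedure-related adverse events occur in more than 15% of patients". The conflict changes neither how events are counted nor the 15% threshold. What suffers is interpretation: the complication rate would be reported for a procedure whose power limit the protocol does not state consistently.

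This is not a claim that safeguards are absent. Both sections cap temperature at about 60°C, and Section 4.2 has a rule for stopping or reducing power.

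**Working it through.** No sample-size, power or error-rate figure bears on this point. The check is a comparison of two stated rules, followed by a search for anything that settles the difference.

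**Step 1: do both rules concern the same device and step?** Yes. Both sections describe a retractable needle-tipped catheter, and Section 4.2 delivers the energy through the needle. The standard catheter has its own, separate 30–50 W sentence earlier in Section 4.2, so the needle range is not that sentence misread.

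**Step 2: compare the two, item by item.**

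| Item | Section 4.1 | Section 4.2, needle paragraph | Agree? |
|---|---|---|---|
| Duration | 60 to 90 s | 60–90 s | Yes |
| Temperature cap | 60°C | below 60°C | In substance |
| Infusion before energy | 1 mL/min for 60 s | 1 mL/min for 60 s | Yes |
| Power | below 35 W | 30–50 W | No |
| Control | temperature-controlled | manual titration | Wording differs |

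**Step 3: test each power band against both rules.**

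| Delivered power P | 4.1 rule (P < 35) | 4.2 rule (30 ≤ P ≤ 50) |
|---|---|---|
| Below 30 W | met | outside the range, except on down-titration |
| 30 W to just under 35 W | met | met |
| 35 to 50 W | breached | met |
| Above 50 W | breached | breached |

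- Difference between upper limits: 50 − 35 = 15 W.
- Width of the Section 4.2 range: 50 − 30 = 20 W.
- Part of that range barred by Section 4.1: 15 / 20 = 75%.
- Part of that range meeting both rules: (35 − 30) / 20 = 5 / 20 = 25%.

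The 75% is a share of the permitted range, not of applications. The documents give no distribution of delivered power.

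**Step 4: does any other text settle it?** No. The sentence in Section 10.3 can refer to either part of Section 4, and Section 13.3 has no precedence rule. Both power sentences are intact, current body text.

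**Secondary points.** Some steps appear in only one section. Section 4.1 alone has the contrast injection and position check ("Myocardial staining with contrast is confirmed with fluoroscopy to ensure intramyocardial positioning and to rule out perforation") and the heparin in the infused saline. Section 4.2 alone has the rule for stopping or reducing power. These are omissions to clarify, not contradictions.

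**The case against.** The strongest counter-reading is that Section 4.1 is device description in the present tense, while Section 4.2, written as what will be done, is the operative procedure. This does not hold up. Section 4.1 sits under a heading covering devices and procedures, gives stepwise instructions at target sites, and is not marked as background. If it were not operative, the contrast check against perforation would have no operative statement, because it appears nowhere else. The reference in Section 10.3 to hardware and software also echoes the title of Section 4.1, so the textual cues point in opposite directions.

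Three other objections stand in part.

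- **The rules overlap.** An operator who stays between 30 W and just under 35 W satisfies both power limits. The conflict lies in the upper limit and the 35–50 W band. Powers below 30 W are also treated differently by the two sections.
- **The control-mode difference is weaker than the wattage difference.** Section 4.2 also limits temperature while power is titrated, so the two phrases may loosely describe one practice. This needs clarifying, but the wattage conflict does not depend on it.
- **No planned analysis changes.** Section 17 plans only percentages, means and standard deviations, with no per-protocol set, and complications count at any delivered power. The harm is to judging adherence and to describing the treatment, not to a computed result.

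Sections 4.1 and 4.2 can also be read as complementary for steps stated only once, which is why the contrast, heparin and stopping points are kept secondary.

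**Conclusion.** The concern holds, and the text must be fixed before the protocol can serve as a single standard for needle applications. The ceiling on power through the investigational needle is below 35 W in one section and 50 W in the other, and nothing in the documents says which governs. The affected band is 35–50 W.

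The conclusion rests on the text alone and needs no outside figure. It assumes only that both sections are operative, since neither is marked otherwise. How often the conflict would arise in practice, and whether it would alter the complication rate, cannot be determined from the documents.

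**What to change.** The sponsor must reconcile Sections 4.1, 4.2 and 10.3 so that the needle power limit is stated once and Section 10.3 points to that statement. Which limit applies is for the sponsor to decide with its clinical and device experts; no setting is proposed here.

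The same amendment should clarify the control mode, the infusate and the position check before energy delivery, and should say whether the rule for stopping or reducing power covers every needle application.

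Maximum delivered power per needle application should be recorded so that adherence can be judged. The case report form is not among the documents, and Section 17 already plans to collect procedural characteristics, so this may be in place.

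The cost is a text amendment and, only if not already captured, one recorded value per application. No additional patients or visits are needed.

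### Sections 4.1 and 4.2 set different maximum powers for the needle catheter (<35 W against 50 W), and nothing in the protocol says which governs

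*Combined protocol and SAP*

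**What the plan says.** Section 4.1 describes the needle catheter and ends with operating steps: needle depth, contrast injection, a fluoroscopic check for perforation, then energy delivery. The delivery step reads: "Temperature-controlled power is delivered for 60 to 90 s with temperature limited to 60°C and power limited to <35 W".

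Section 4.2 has separate paragraphs for standard and needle ablation. Under the needle heading it says: "Power will be manually titrated between 30-50 W (limiting catheter tip temperatures to < 60°C) over 60-90 seconds". It also tells the operator to stop or reduce power on a sudden temperature rise or a rapid impedance change. The standard catheter has its own sentence ("For unipolar RF, power will be set to 30–50 W at 30-cm³ irrigation"), so the needle figure is not a misread setting for the other device.

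Section 10.3 sends a patient to needle ablation when standard ablation does not eliminate the arrhythmia or has already failed. It adds: "The INA hardware/software will be employed as described above". It gives no section number and no power.

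Section 13.3 restricts departures from the protocol: "The investigator will not deviate from the protocol except in medical emergencies or in unforeseen, isolated instances".

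**The concern.** Power and duration set how much energy the investigational device can deliver. Two sections describe the same retractable needle catheter, with the same duration and a 60°C limit, but give different maximum powers. No section ranks one above the other, or assigns either to a phase, an arrhythmia type or a step-up rule.

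The first consequence is for adherence. At 40 W the operator complies with 4.2 and departs from 4.1, so a monitor applying Section 13.3 cannot classify the application.

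The second is for interpretation. Procedural complications and 6-month freedom from arrhythmia are the co-primary endpoints, and Section 17 reports them as simple percentages. If some patients are treated under one ceiling and some under the other, those percentages describe a device setting that the protocol does not pin down. Total needle ablation time is a secondary endpoint, but power is not among the endpoints. The listed outcomes would therefore not show afterwards who was treated above 35 W.

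**Working it through.** The plan computes nothing on this point, so there is no figure of its own to reproduce. The check compares the two settings directly.

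**Inputs**

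| Item | Section 4.1 | Section 4.2, needle paragraph |
|---|---|---|
| Power | <35 W | 30 to 50 W |
| Duration | 60 to 90 s | 60 to 90 s |
| Temperature | limited to 60°C | tip below 60°C |
| Control | temperature-controlled | manually titrated, with a temperature limit |

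**Step 1: overlap.** Both rules are met when power P satisfies 30 ≤ P < 35 W. That is 35 − 30 = 5 W of a 50 − 30 = 20 W range, so 5/20 = 25%.

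**Step 2: conflict.** Settings with 35 ≤ P ≤ 50 W are allowed by 4.2 and barred by 4.1. That is 50 − 35 = 15 W, so 15/20 = 75% of the 4.2 range. This is a share of the permitted range. It does not predict how often operators would go there.

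**Step 3: ceiling.** 50 − 35 = 15 W and 50/35 = 1.43, so the 4.2 maximum is about 43% higher.

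**Step 4: upper bound on energy** (power × time, assuming maximum power is held throughout).
- 4.1: just under 35 × 60 = 2,100 J, to just under 35 × 90 = 3,150 J.
- 4.2: 50 × 60 = 3,000 J, to 50 × 90 = 4,500 J.

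The temperature limit and the 4.2 rule for cutting power mean that delivered energy will often be lower. These figures are ceilings, not expected doses.

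**Step 5: patients.** Section 8 expects 200 enrolled and a 66% screen failure rate: 200 × (1 − 0.66) = 68, which the plan rounds to about 70 needle patients. This is the most that could be affected. Only patients with an application at 35 W or more would breach 4.1, and the documents give no basis for estimating that number.

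**The case against.** **Section 4.2 is the operative text.** It is the section on procedures and says what will be done, whereas 4.1 is headed as a hardware description and is written in the present tense. This has some force, and it is a reason not to assume that 4.1 wins. It does not remove the conflict, because the last paragraph of 4.1 gives operating steps and a numerical limit.

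**Section 4.1 covers VT only.** Its delivery paragraph opens with VT circuit sites. But 4.2 covers all ventricular arrhythmias, including VT, so VT cases still have two ceilings.

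**An operator can comply with both.** This is correct: 30 to <35 W satisfies each section. The dispute is about the maximum, and nothing tells the operator to stay in that band.

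**Existing safeguards suffice.** The temperature limit and the 4.2 stop rule lower the risk, but they do not set a maximum power.

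**The control modes may not differ.** Manual titration to a temperature limit can be read as a form of temperature control, and neither section clearly names a generator mode. This stands: the mode needs clarifying, but it is not a second proven contradiction.

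**The analysis is descriptive and dose would vary anyway.** Individual titration over 30 to 50 W would produce different doses even without 4.1. That limits the effect on interpretation. It leaves the adherence problem untouched.

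**Conclusion.** The inconsistency is real and should be corrected. The two sections differ by 15 W (43%) in maximum needle power, and 75% of the 4.2 range is barred by 4.1. Confidence is high for the mismatch in the text. It does not extend to clinical consequences, since the documents give no lesion or complication data by needle power.

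A reader might infer more than the documents support:

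- *That Section 10.3 imposes the 4.1 limit on every needle case, so that all of the roughly 70 patients are affected.* Section 10.3 speaks of equipment and names no section, and 4.2 also lies above it. The number affected is unknown.
- *That 35 W must be the intended limit because it is stricter.* Nothing in the documents shows which value the sponsor meant.
- *That the needle range was wrongly copied from the irrigated standard catheter.* The ranges coincide, but the needle's 1 mL/min for 60 s is an infusion before energy delivery, and no rate during delivery is given, so the irrigation figures are not comparable. The introduction's remark on cooling ("A larger interface between catheter tip and blood improves cooling and allows for the delivery of more power without a rise in impedance") concerns larger surface tips; applying it to a needle in muscle is inference.
- *That an epicardial needle limit is part of this conflict.* The esophageal monitoring rule does mention needle use there ("when ablation is performed in the coronary sinus or epicardium irrespective of whether standard ablation or intramural needle ablation is performed"), but a missing epicardial limit would be a separate omission.
- *That safety stopping fails.* The rule in Section 11 depends on severe procedure-related events in more than 15% of patients, not on power, and works under either ceiling.

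**What to change.** 1. The sponsor confirms, from its device data, the intended maximum needle power and the control mode.
2. That single limit and mode are stated in both 4.1 and 4.2, and 10.3 cites them by section number. The duration, the 60°C limit and the 4.2 rule for stopping or cutting power stay as they are.
3. Until this is confirmed, needle power is set within 30 to <35 W, which meets both sections. The 4.2 rule for reducing power still applies.
4. The case report form records the maximum power of each needle application.
5. If patients have already been treated, report how many had at least one application at 35 W or more.

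The cost is a sentence in each of 4.1 and 4.2, a cross-reference in 10.3 and one data field. No patient is excluded and no visit or test is added. The possible downside, during the interim period or permanently if the lower limit is confirmed, is that a <35 W cap might make smaller lesions in patients whose arrhythmia has already resisted standard ablation. The documents give no data on this, which is why the sponsor's device data must decide the final value.
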